5.2 Assessment of Safety

The safety plan for patients in this study is based on clinical experience with atezolizumab in completed and ongoing studies. The anticipated important safety risks are outlined below.

Measures will be taken to ensure the safety of patients participating in this study, including the use of stringent inclusion and exclusion criteria and close monitoring of patients during the study. Administration of atezolizumab will be performed in a monitored setting in which there is

immediate access to trained personnel and adequate equipment and medicine to manage potentially serious reactions (See Table 2). Guidelines for managing patients who experience anticipated adverse events, including criteria for treatment interruption or discontinuation, are provided in Section 7.4. Refer to Section 9 for details on safety reporting (e.g., adverse events, pregnancies) during the study.

5.2.1 Risks Associated with Atezolizumab

Atezolizumab has been associated with risks such as the following: IRRs and immune-related hepatitis, pneumonitis, colitis, pancreatitis, diabetes mellitus, hypothyroidism, hyperthyroidism, adrenal insufficiency, hypophysitis, Guillain-Barré syndrome, myasthenic syndrome or myasthenia gravis, facial paresis, myelitis, meningoencephalitis, pericarditis, pericardial effusion, cardiac tamponade, myocarditis, pericardial disorders, nephritis, and myositis. Immune-mediated reactions may involve any organ system and may lead to hemophagocytic lymphohistiocytosis and macrophage activation syndrome. Refer to Section 6 of the Atezolizumab Investigator's Brochure for a detailed description of anticipated safety risks for atezolizumab.

5.2.2 Patient Discontinuation from Study

Patients have the right to voluntarily withdraw from the study at any time for any reason. In addition, the investigator has the right to withdraw a patient from the study at any time. Reasons for withdrawal from the study may include, but are not limited to, the following:

- Withdrawal of consent
- Study termination or site closure
- Death
- Loss to follow up

Every effort should be made to obtain information on patients who withdraw from the study. The primary reason for withdrawal from the study should be documented in the patient's medical records. If a patient requests to be withdrawn from the study, this request must be documented in the source documents and signed by the investigator.

If a patient withdraws from the study, the study staff may use a public information source (e.g., county records) to obtain information about survival status.

5.3 Treatment and Patient Discontinuation

Patients must permanently discontinue study treatment (atezolizumab) if they experience any of the following:

- Intolerable toxicity related to study treatment, including development of an immune-mediated adverse event determined by the investigator to be unacceptable given the individual patient's potential response to therapy and severity of the event
- Any medical condition that may jeopardize the patient's safety if he or she continues study treatment
- Investigator discretion
- Use of another non-protocol anti-cancer therapy
- Pregnancy
- Loss of clinical benefit as determined by the investigator after an integrated assessment of radiographic and biochemical data, local biopsy results (if available), and clinical status (e.g., symptomatic deterioration such as pain secondary to disease). In the adjuvant setting, any documented recurrence of tumor will be considered a treatment failure qualifying the patient for discontinuation of the study

The primary reason for study treatment discontinuation should be documented in the patient's medical records. Patient who discontinue treatment will be proceed with SoC treatment. In the neo-adjuvant setting, patient will proceed to definitive surgery with or without adjuvant therapy. In the adjuvant setting, patients will complete their adjuvant course of adjuvant radiation or chemoradiation or continue with routine surveillance. Patients who discontinue study treatment prematurely will be replaced.

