All participants will undergo a curative-intent surgical resection as defined by SoC. Surgery will occur within 10 weeks of study enrollment and at least two weeks after second dose of neoadjuvant Atezolizumab. The goal of curative intent surgery for regionally metastatic CSCC involves resection to negative margins of the index lesion with the associated at-risk regional lymph nodes as determined by the study physician. An evaluation of tumor status and staging per AJCC guidelines (8th edition) will be performed on all surgical specimen. The pathologist will assess the specimen for pCR and mPR (see 10.1). Pathology assessment will be as per standard of care documentation, including: dimensions of index lesion, total nodal number of lymph nodes removed, total positive node number (and positive nodal levels), any extracapsular extension, any perineural invasion. PD-L1 staining will be performed on a representative section from the largest positive node. Tissue will be formalin fixed and paraffin embedded and banked per standard pathology protocol.

Patients demonstrating pCR at time of surgery:*Adjuvant Treatment*

Patients demonstrating pCR at the time of surgery will not receive any additional adjuvant therapy and will enter surveillance.

Imaging

PET/CT will be performed approximately 12 weeks after surgery.

Follow-up / Surveillance

Patients will be followed in otolaryngology/head and neck surgery and medical oncology clinic every 3 months for 3 years after surgery. Patients will be assessed for treatment-related side effects, cancer recurrence and blood draws performed at the cancer center for biomarkers.

In the setting of suspected clinical or radiographic recurrence per iRECIST criteria, tumor tissue will be collected by biopsy, unless not clinically feasible as assessed and documented by the investigator.

Patients with residual disease at time of surgery:

Patients with residual disease at the time of surgery will receive atezolizumab Q3W x 15 cycles in combination with SoC adjuvant radiation. SoC adjuvant radiation will be initiated greater than 4 weeks and less than 7 weeks after surgery and consists of 6 weeks of radiation therapy with dosimetry determined by pathologic findings at the time of surgery. Recommendations for adjuvant treatment will be determined at a multidisciplinary tumor board where surgical pathology findings will be reviewed. Adjuvant atezolizumab will begin concurrent to adjuvant radiation and continue for 15 cycles.

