10. STATISTICAL CONSIDERATIONS

10.1 Study Design and Overview of Primary and Secondary Endpoints

This is a Phase II single-arm trial investigating the efficacy of the anti-PD-L1 antibody atezolizumab (Genentech) in the neoadjuvant setting for patients with regionally metastatic cutaneous head and neck squamous cell carcinoma with a historic or unknown primary. This will be an open-label trial reporting response rates with pCR as the primary endpoint.

Due to the nature of single arm and small sample size, we will not adjust our analyses for multiplicity, but we will present all outcomes we studied in the single paper with pre-specified designation of each outcome (e.g., primary or secondary/exploratory). Also, formal hypothesis testing will be avoided or properly accompanied/indicated by warning (e.g., a historical control for comparator or other comparability issues).

We will summarize continuous data at baseline with standard descriptive statistics, e.g., mean and SD (or median and IQR) and binary data with frequency and proportion. For continuous and binary outcomes data, point estimates and 95% CIs will be computed for appropriate parameter estimable (e.g., mean or median with accounting for censoring, if needed) and the Clopper and Pearson exact binomial method (with no censoring), respectively.

Primary Endpoints

Pathologic Complete Response (pCR)

pCR is defined as having no residual invasive squamous cell carcinoma within the primary tumor and all resected lymph nodes as assessed by the pathologist at the time of primary resection. The rate of pCR is defined as the proportion of patients demonstrating pCR.

Major Pathologic Response (mPR)

mPR is defined as having $\leq 10\%$ residual invasive squamous cell carcinoma within the primary tumor and all resected lymph nodes as assessed by the pathologist at the time of primary resection. The rate of mPR is defined as the proportion of patients demonstrating mPR.

Event Free Survival (EFS)

EFS is defined as the time from randomization to the first day of the any of the following events:

- Radiographic evidence of recurrence or disease progression per iRECIST
- Clinical evidence of recurrence or disease progression as assessed by clinical exam and confirmed by biopsy.
- Death due to any cause

A non-parametric Kaplan-Meier (KM) method will be used to estimate the 2-year EFS curve. Participants who do not experience recurrence or disease progression at the time of their last

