10.2 Sample Size Estimation / Evaluation of Efficacy / Accrual Rate

A Simon's two-stage design is used to calculate an optimal sample size and minimal efficacy threshold using a primary end-point of pCR. We assume an alpha type I error of 0.05 and power of 80% and set our response probability for an ineffective drug (p_0) at $pCR < 0.05$ and our response probability of an effective drug (p_1) at $pCR > 0.30$.

Sample Size

Given these parameters, a total of 18 subjects (n) with 3 or more responses would support continued investigation of the proposed treatment paradigm.

Evaluation of Efficacy

In stage 1 of our study, 5 (n_1) patient will be enrolled and if no responses are observed, the trial will be stopped early for futility.

Accrual Rate

We estimate an accrual of 1-2 patients per month, with a goal accrual of 18 patients in this trial

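### Section 5.3 replaces every patient who stops atezolizumab early and no pCR analysis set is defined, so the plan permits known non-pCR patients to drop out of the primary count after surgery

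*Combined protocol and SAP*

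**What the plan says.** Section 5.3 lists the grounds for permanently stopping atezolizumab in both treatment phases and closes with an unqualified rule: "Patients who discontinue study treatment prematurely will be replaced". One listed ground belongs to the adjuvant phase: "In the adjuvant setting, any documented recurrence of tumor will be considered a treatment failure qualifying the patient for discontinuation of the study". For patients who stop before surgery, the same section says: "In the neo-adjuvant setting, patient will proceed to definitive surgery with or without adjuvant therapy".

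Section 3.1 sets out who can receive adjuvant drug. For responders: "Patients demonstrating pCR at the time of surgery will not receive any additional adjuvant therapy and will enter surveillance". For patients with residual disease: "Adjuvant atezolizumab will begin concurrent to adjuvant radiation and continue for 15 cycles".

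On counting, section 10.1 says: "The rate of pCR is defined as the proportion of patients demonstrating pCR". Section 10.2 sets the final rule, that "a total of 18 subjects (n) with 3 or more responses would support continued investigation of the proposed treatment paradigm", and for the first stage of five says: "patient will be enrolled and if no responses are observed, the trial will be stopped early for futility". Neither section says whether a replaced patient stays in the denominator. The only population rule is in section 9.1, where at least one dose makes a patient eligible for adverse event reporting. It does not address pCR.

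**The concern.** In its ordinary sense, replacing a patient in a fixed-size design means that a new patient takes the old one's place among the 18. If that is done for patients who have been treated and scored, it is a post-treatment exclusion on the primary endpoint.

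After surgery the exclusion is not neutral. Responders get no adjuvant drug and so cannot discontinue it. Everyone who can is a known non-pCR, and one of the grounds for stopping is recurrence. A non-pCR patient taken out and exchanged for a new patient, who has some chance of pCR, can only raise the counted rate.

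Two things are at stake: the reported pCR rate, and the chance of meeting the rule of 3 or more in 18 when the drug is ineffective.

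**Working it through.** **Inputs.** From the synopsis and section 10.2: null rate 0.05, target rate 0.30, five patients in stage 1, stop if none respond, 18 in total, success at 3 or more pCR. Not given in the documents, so assumed: the share *d* of non-pCR patients who stop adjuvant drug and are replaced, taken as 5% to 30%.

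**1. Reproduce the design.** With *b* the binomial probability and *p* the true rate,

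P(success) = Σ over x = 1…5 of b(x; 5, p) × P(Bin(13, p) ≥ 3 − x).

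- p = 0.05: 0.2036 × 0.1354 + 0.0214 × 0.4867 + 0.0012 = 0.0276 + 0.0104 + 0.0012 = 0.039.
- p = 0.30: 0.3602 × 0.9363 + 0.3087 × 0.9903 + 0.1631 = 0.3372 + 0.3057 + 0.1631 = 0.806.

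Both agree with the stated limits of 0.05 and 80%. The attained 0.039 lies below 0.05 because the count is discrete.

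**2. When the rule can bite.** Section 3.1 starts adjuvant treatment more than 4 and less than 7 weeks after surgery. Fifteen doses three weeks apart put the last dose 14 × 3 = 42 weeks after the first, so up to about 49 weeks after surgery. pCR is known from the surgical specimen, so any adjuvant discontinuation comes after the endpoint is known. Stage 1 needs only five pathology results and would normally be decided before such replacements. The main case therefore fixes stage 1 on the first five patients.

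**3. Counted rate.** If each non-pCR patient is replaced with probability *d* and responders are all kept, the pCR probability among counted patients is

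q = p / (p + (1 − p)(1 − d)).

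For p = 0.05 and d = 0.10: 0.05 / (0.05 + 0.95 × 0.90) = 0.05 / 0.905 = 0.0552.

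**4. Type I error.** With stage 1 fixed, let x be the pCRs among the first five and k the non-pCR patients among them who stay counted. The other 18 − x − k places are filled at rate q:

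P(success) = Σ over x = 1…5 of b(x; 5, p) × Σ over k of b(k; 5 − x, 1 − d) × P(Bin(18 − x − k, q) ≥ 3 − x).

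For comparison, if replacement also reached stage 1, put q for p in the formula of step 1.

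| d (assumed) | q | Stage 1 fixed | Both stages |
|---|---|---|---|
| 0 | 0.0500 | 0.039 | 0.039 |
| 5% | 0.0525 | 0.043 | 0.044 |
| 10% | 0.0552 | 0.047 | 0.050 |
| 20% | 0.0617 | 0.056 | 0.065 |
| 30% | 0.0699 | 0.068 | 0.087 |

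With stage 1 fixed, 0.05 is passed between 10% and 20%.

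**5. Reported rate.** For p = 0.30, the average rate among counted patients is 0.30 / (0.30 + 0.70 × 0.90) = 0.30 / 0.93 = 0.32 at d = 10%, and 0.30 / (0.30 + 0.70 × 0.80) = 0.30 / 0.86 = 0.35 at d = 20%.

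**6. Neutral case.** If replacement is unrelated to pCR, q = p and type I error stays 0.039.

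**7. If replaced patients stay and replacements are added.** The count becomes 18 + k, for which the plan gives no rule. Keeping the threshold at 3 with the extra patients in stage 2 (13 + k in the formula of step 1) gives 0.043, 0.047 or 0.052 for k = 1, 2 or 3.

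**The case against.** The best reply is that no sentence takes a replaced patient out of the pCR count. The synopsis speaks of patients accrued and section 10.2 of patients enrolled, and pCR is judged on the surgical specimen. Section 8 lets patients who stop drug remain in follow-up, and section 5.1.4 continues their tumor assessments, so stopping drug is not leaving the study. All of this stands. A reader might infer that the protocol orders non-pCR patients to be removed, and the documents do not support that. They leave the denominator undefined. Keeping everyone does not settle the matter either: replacements would then take the count beyond 18, while section 12.2 asks the principal investigator to prevent over-accrual.

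A second reply is that stage 1 would be decided before any adjuvant stopping. This also stands, and it is why the stage-1-fixed column is the one to use. The larger figures would require a 0-of-5 result to be held open or reopened.

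A third is that the effect is modest, the rates are assumed, and section 10.1 plays down formal testing. This is fair, but it makes the bias in the reported rate (step 5) matter more, and the go-ahead rule of 3 in 18 still applies.

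Finally, the one-way argument is strict only after surgery. Patients who stop earlier still go to surgery and can be pCR or non-pCR. They yield an endpoint, so they need no replacement for it.

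**Conclusion.** The point holds as an ambiguity with a one-way risk. The replacement rule is unqualified, no pCR set is named, and after surgery the rule can reach only known non-pCR patients. If it is applied to the final count with stage 1 settled on the first five, type I error goes from 0.039 to about 0.043, 0.047, 0.056 or 0.068 when 5%, 10%, 20% or 30% of non-pCR patients are replaced. A true rate of 0.30 reads on average as about 0.32 or 0.35 at 10% or 20%.

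These sizes rest on assumed replacement shares and on replaced patients leaving the count. A reader might infer that the trial's type I error exceeds 0.05. The documents do not show this: in the main case it takes a share above 10%, and with pCR-neutral replacement there is no inflation. The change should be made because the risk falls on the sole primary endpoint and is cheap to remove.

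**What to change.** In sections 5.3 and 10.2, state that any patient who received at least one neoadjuvant dose of atezolizumab is not replaced for the pCR analysis and stays in the two-stage count (five, then 18). Such a patient is scored on surgical pathology, or as non-pCR if not operated. Limit replacement to patients never dosed. Scoring unoperated patients as non-pCR is one convention among several, but it should be fixed in advance. The one-dose threshold matches the safety rule in section 9.1.

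The cost is wording only, with a possibly slightly lower reported pCR rate. Keeping adjuvant stoppers costs no power: they are already non-pCR within the true rate, so power stays 0.806 at a true all-treated rate of 0.30.

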Simon's two-stage design (Simon, 1989) was used to determine sample size. The null hypothesis that the true response rate (pCR) is $p_0 = 0.05$ will be tested against a one-sided alternative. In the first stage, 5 patients will be accrued. If there are no responses in these 5 patients, the study will be stopped. Otherwise, 13 additional patients will be accrued for a total of 18. The null hypothesis will be rejected if 3 or more responses are observed in 18 patients. This design yields a type I error rate of 0.05 and power of 80% when the true response rate is 0.3.

Due to the nature of single arm and small sample size, we will not adjust our analyses for multiplicity but we will present all outcomes we studied in a single paper with a pre-specified designation of each outcome (e.g., primary or secondary/exploratory). Also, formal hypothesis

testing will be avoided or properly accompanied/indicated by a warning (e.g., a historical control for comparator or other comparability issues).

We will summarize continuous data at baseline with standard descriptive statistics, e.g., mean and SD (or median and IQR) and binary data with frequency and proportion. For continuous and binary outcomes data, point estimates and 95% CIs will be computed for appropriate parameter estimable (e.g., mean or median with accounting for censoring, if needed) and the Clopper and Pearson exact binomial method (with no censoring), respectively.

Longitudinal data will be summarized similarly and accompanied by time point to illustrate possible trends. When we utilize historical controls (for description and informal comparison), we will use control sample matched on key confounders (e.g., age, gender, key comorbidities and medical histories). We expect approximately 40 control patients, thus, achieving approximately 1:2 ratio in sample size for current sample: comparator.

Endpoints

Primary Endpoint

pCR

Secondary Endpoints

- 1) Oncologic response to therapy:
 - a) MPR
 - b) 2-year EFS
- 2) Imaging and biomarker assessment of response to therapy:
 - a) FDG avidity of nodal disease sites as measured by PET
 - b) ORR as measured by CT or MRI of the head and neck per iRECIST criteria
 - c) Plasma exosome levels
- 3) Safety and Tolerability assessment:
 - a) Toxicity (adverse events) determined by CTCAE v5

Duration of Study and Follow-up

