Because of the possibility of an initial increase in tumor burden caused by immune cell infiltration in the setting of a T-cell response (termed pseudoprogression) with atezolizumab treatment, clinical or radiographic progression per iRECIST may not be indicative of true disease progression. In the absence of unacceptable toxicity, patients with clinical or radiographic evidence of progression while receiving neo-adjuvant atezolizumab will be permitted to receive their second dose and postoperative adjuvant doses of atezolizumab if they meet all of the following criteria:

- Evidence of clinical benefit, as determined by the investigator following a review of all available data
- Absence of symptoms and signs (including laboratory values, such as new or worsening hypercalcemia) indicating unequivocal progression of disease
- Absence of decline in Performance Status that can be attributed to disease progression
- Absence of tumor progression at critical anatomical sites (e.g., leptomeningeal disease) that cannot be managed by protocol-allowed medical interventions

Patient who have NOT met all of the above criteria will NOT receive their second dose of neo-adjuvant atezolizumab and will proceed directly to surgery. These patients will also not receive adjuvant atezolizumab and will receive only SoC adjuvant radiation.

Pre-Dose Blood Draws

Participants will undergo blood draws at the infusion center prior to administration of neo-adjuvant atezolizumab for routine blood analysis as noted in section 5.1.5. One 4 mL lavender-top tube will be drawn simultaneously with these scheduled blood draws for research analysis of tumor-associated exosomes. This research vial will be transported by [name], [name], [name], or other approved Otolaryngology department members to the Cancer Center Biorepository for cataloging (contact: [name]), and storage as needed. Collected whole blood samples will be withdrawn and processed by [name] and collaborators when needed for subsequent analysis.

Post-neo-adjuvant Imaging

Repeat fine-cut contrast-enhanced CT or MRI imaging of the head and neck will be performed one week prior to surgery to assess response to neo-adjuvant therapy. The imaging modality utilized will be the same as that modality used for screening.

Surgery and Pathologic Evaluation

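### Section 5.3 replaces every early stopper, including adjuvant-phase patients already known to be non-pCR, and the plan does not say whether replaced patients still count in the 18

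*Combined protocol and SAP*

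**What the plan says.** Section 5.3 equates study treatment with atezolizumab, deals with the neoadjuvant and adjuvant settings together, and ends: "Patients who discontinue study treatment prematurely will be replaced". The listed grounds for stopping include toxicity, investigator discretion and loss of clinical benefit. It adds: "In the adjuvant setting, any documented recurrence of tumor will be considered a treatment failure qualifying the patient for discontinuation of the study".

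Section 3.1 divides patients by the primary outcome. On one side: "Patients demonstrating pCR at the time of surgery will not receive any additional adjuvant therapy and will enter surveillance". On the other: "Patients with residual disease at the time of surgery will receive atezolizumab Q3W x 15 cycles in combination with SoC adjuvant radiation".

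Before surgery, patients with progression who fail the Section 3.1 criteria for continuing "will NOT receive their second dose of neo-adjuvant atezolizumab and will proceed directly to surgery". Section 5.3 sends other neoadjuvant stoppers to surgery too, and Section 3.1 states: "All participants will undergo a curative-intent surgical resection as defined by SoC". Pathology should therefore normally be available for them.

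Section 10.1 defines the endpoint: "The rate of pCR is defined as the proportion of patients demonstrating pCR". The Protocol Synopsis gives the decision rule: "The null hypothesis will be rejected if 3 or more responses are observed in 18 patients", after a futility stop if there is no response in the first 5. Neither Section 10.1 nor Section 10.2 names the set of patients counted. Section 9.1 does define a treated population (consent and at least one dose), but only for adverse event reporting.

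**The concern.** Replacement is harmless to a response rate when it is unrelated to response. Here, in the adjuvant phase, it cannot be unrelated: a patient with pCR receives no adjuvant drug and so cannot stop it. Nor does replacement fill a gap in the primary endpoint, because pCR is read at surgery, before the first adjuvant dose.

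If replaced patients leave the 18, known failures are exchanged for new patients who may respond. The pCR estimate, its exact confidence interval and the chance of reaching 3 of 18 all move upward with no change in drug activity. If replaced patients stay, the number analysed exceeds 18 and the cut of 3 was not derived for it. The plan does not say which applies, so the choice could be made after the results are known.

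**Working it through.** **Inputs from the plan.** Protocol Synopsis and Section 10.2: n1 = 5, stop if 0 pCR; N = 18, reject if at least 3 pCR; p0 = 0.05; p1 = 0.30; type I error 0.05; power 80%.

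**Assumed input.** g, the share of non-pCR patients who stop early and are replaced. The documents give no value; 5%, 10% and 20% are shown.

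**Step 1: reproduce the design.** P(reject) = Σ over x = 1 to 5 of P(X1 = x; 5, p) × P(X2 ≥ 3 − x; 13, p).

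At p = 0.05:
- x = 1: 0.20363 × 0.13542 = 0.02758
- x = 2: 0.02143 × 0.48666 = 0.01043
- x ≥ 3: 0.00116
- Sum: 0.0392

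At p = 0.30 the sum is 0.806. The stated design reproduces; 0.05 is the ceiling and 0.0392 the attained value. The stage 1 stop probability at p0 is 0.95^5 = 0.774.

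**Step 2: results dropped, both stages affected (upper bound).** The pCR rate among those counted is q = p / [p + (1 − p)(1 − g)]. For p = 0.05 and g = 0.20: 0.05 / (0.05 + 0.95 × 0.80) = 0.0617. Put q into the Step 1 formula.

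| g | q at true 5% | Type I error | Stage 1 stop | q at true 30% |
|---|---|---|---|---|
| 0 | 5.0% | 0.0392 | 0.774 | 30.0% |
| 5% | 5.2% | 0.0442 | 0.764 | 31.1% |
| 10% | 5.5% | 0.0500 | 0.753 | 32.3% |
| 20% | 6.2% | 0.0652 | 0.727 | 34.9% |

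Type I error reaches 0.05 at g of about 10%.

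**Step 3: results dropped, replacement only after the stage 1 look.** The look uses the first 5 as treated, at rate p. Given x pCRs among them, k of the 5 − x failures are later replaced, each with probability g, and the remaining 13 + k places fill at rate q:

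P(reject) = Σ over x ≥ 1 of P(x; 5, p) × Σ over k of P(k; 5 − x, g) × P(Bin(13 + k, q) ≥ 3 − x).

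At p = 0.05 this gives 0.0427, 0.0466 and 0.0560 for g = 5%, 10% and 20%.

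This is the more realistic timing. Surgery falls within 10 weeks of enrolment. Adjuvant drug starts more than 4 weeks after surgery, and 15 doses at 3-week intervals span 14 × 3 = 42 weeks. Most adjuvant stops should therefore follow a look at the surgical results of 5 patients.

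**Step 4: results kept, N grows, cut stays at 3.** With N − 5 patients in stage 2 at p = 0.05, type I error is 0.0433, 0.0475 and 0.0517 at N = 19, 20 and 21. Power at 0.30 is 0.813, 0.818 and 0.822.

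**Step 5: replacement of some pCR patients too.** A neoadjuvant stopper may have pCR. If 20% of non-pCR and 10% of pCR patients were replaced (assumed) in both stages, q = 0.05 × 0.90 / (0.05 × 0.90 + 0.95 × 0.80) = 0.045 / 0.805 = 0.0559 and type I error is 0.051, not 0.065. Equal shares give no bias.

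**The case against.** Section 5.3 says stoppers are replaced; it does not say their pathology is discarded. Section 10.1 excludes nobody from the proportion, operated patients are assessed for pCR, and Section 8 lets patients who stop the drug stay for follow-up. Counting every operated patient is a fair reading, and on it the design is barely disturbed: type I error stays under 0.05 up to N = 20 and power rises slightly. All of this stands as an argument about size. It does not supply the missing rule.

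A reader might infer that a swap within 18 is intended, because Section 10.2 gives a goal accrual of 18 and Section 12.2 tells the investigator to prevent over-accrual. The documents do not support that. Replacement means enrolling more than 18 on either reading, and neither section says whose results are counted.

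A reader might also infer that every replacement pushes the rate up. That is certain only in the adjuvant phase. Patients who stop before surgery, for toxicity for example, can still have pCR, so losing them can bias in either direction. That progressors barred from dose 2 are non-pCR is plausible, but the plan does not state it.

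The effect is also modest. The plan promises a ceiling of 0.05, not 0.039, and replacement after the look passes that ceiling at the assumed 20% but not at 10%. The shift at a true 30% is small beside the planned exact interval, which for 5 of 18 runs from 9.7% to 53.5%. Section 10.1 says formal testing will be avoided or carry a warning. That makes type I error less central, but the futility stop and the 3-of-18 rule remain, and the reported rate would carry the same bias.

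**Conclusion.** The concern holds as a conditional one. The text is clear that all early stoppers are replaced, that adjuvant-phase stoppers are all known non-pCR, and that no pCR analysis set is defined. What happens to a replaced patient's result is not stated, so the plan permits selection toward pCR but does not prescribe it.

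If results are dropped, mostly after the stage 1 look, type I error at a true 5% is about 0.043, 0.047 or 0.056 when 5%, 10% or 20% of non-pCR patients are replaced. The both-stages figures of 0.044, 0.050 and 0.065 are close to an upper bound. A true 30% would be reported as up to about 31%, 32% or 35%. If results are kept, the effect is smaller still. These sizes rest on assumed stopping rates and on replacement of non-pCR patients only; with no early stopping there is no bias. The point should be corrected because the rule acts on the primary outcome and the correction is nearly free, not because the design is shown to fail.

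**What to change.** Amend Section 5.3 so that no patient who has received at least one neoadjuvant dose is replaced for the pCR analysis, whatever the reason or phase of stopping; replace only patients who never received atezolizumab. State in Section 10.1 that the pCR denominator is all treated patients (the first 5 for stage 1, all 18 for the final test), scored by surgical pathology, or as non-pCR if not resected. Report the number who stopped early, by phase and reason.

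This adds no procedures and no patients. The design keeps its attained type I error of 0.039, and its power of 0.806 provided 0.30 is the rate among all treated patients. The cost is that the observed pCR rate may be lower. If 0.30 was meant as a completers-only rate and 5%, 10% or 20% stop early without pCR, the all-treated rate is 0.30 × 0.95 = 0.285, 0.30 × 0.90 = 0.270 or 0.30 × 0.80 = 0.240, and power falls to 0.780, 0.751 or 0.682. The sponsor should say which population 0.30 describes.
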